#### 9.2 STUDY ASSESSMENTS

#### **INFORMATION VISIT** (screening visit)

#### Conducted between Week 12 and 28+0 weeks gestation

Women attending as described in paragraphs 5.1 to 5.3 and who meet the initial eligibility criteria will be provided with a copy of the Patient Information Leaflet, given the opportunity to discuss the study and to ask any questions. The inclusion / exclusion checklist will be used as a guide to eligibility at this stage, and may be completed in part, if wished. After the woman has had the opportunity to consider whether she would like to participate, if she declines minimal details will be collected and added to the study screening log and the reason for declining collected.

If she verbally agrees she will be invited to give written consent to the study (witnessed if required as described above) and be randomised.

#### CONSENT

Women who are eligible and wish to participate (as described in paragraph 5.4 above) will be asked to sign a consent form. Eligibility will be formally confirmed by a suitably trained and delegated clinician. The original consent form(s) will be stored in the Investigator Site File (ISF) file, a copy is given to the woman, a copy added to the medical notes.

The consent log will be updated via the eCRF and following completion of the consenting procedures the following baseline assessments will be performed on participating women:

- Demographics
- Medical History including current pregnancy details, previous pregnancies, Height, Weight and Vital signs
- Preferred contact information

#### RANDOMISATION

Randomisation will occur after eligibility has been confirmed and consent has been given. Women will then be randomised and assigned to one of the study treatments either metformin or placebo.

A prescription will be issued for dispensing of the IMP. Medication will be dispensed in HDPE plastic bottles with sufficient supply for 4 weeks of treatment. A date for starting treatment should be agreed with the participant, and this should be no later than 48 hours after randomisation.

Women should be informed that after they take the medication that they may see a complete tablet in their stool (the placebo is designed to have the same effect). This is normal this is an empty shell of the tablet which is harmless and it indicates that the tablet has passed through her intestine correctly.

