# 7. RANDOMISATION

#### 7.1 Randomisation Procedures

Participants will be randomised to treatment (active or placebo) in a 1:1 ratio. Recruiting centre will be the only stratification variable, using simple randomisation under a randomly permuted block design. Randomisation codes will be provided by ECTU to ISG and packs dispensed in a sequential fashion. Details of the study pack number allocated will be recorded in the participant's medication record as well as in the drug accountability logs.

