# 8.1.3 Labelling and Packaging

Both the active and placebo treatments will be labelled and packaged in high density polyethylene (HDPE) bottles by Investigational Supplies Group (ISG), [name] in accordance with the Pharmacy, Medicines and Poisons Board (PMPB). Drugs will be supplied in bottles each containing Glucophage 500 mg slow release tablets or placebo sufficient bottles for one month supply will normally be dispensed to a participant at any one time.

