# 8.3 DOSING REGIME

Women will be prescribed metformin tablets in an incremental dose starting at 500mg (1 tablet per day) increasing over four weeks up to 2000mg (4 tablets per day).

First dose will be administered following consent (first visit between 12 and 28 weeks gestation). Women will be asked to start (week 1) with 500mg metformin (1 tablet, once daily) taken with food in the evening, increasing in week 2 to total daily dose of 1000mg per day (2 tablet, one in the morning and one in the evening daily). In week 3: there will be a further increment to a total daily dose of 1500mg per day (3 tablets, one in the morning and two in the evening daily). In week 4 there will be a final increment to a total daily dose of 2000mg (4 tablets, two in the morning and two in the evening daily). Thereafter treatment is planned to continue at 2000 mg (4 tablets) until women have delivered their baby or met one of the criteria described paragraph 5.9.

Week	Morning Tablets (500mg each)	Evening Tablets (500mg each)
Week 1	0	1
Week 2	1	1
Week 3	1	2
Week 4	2	2
Week 5	2	2

If side effects (largely anticipated to be gastro-intestinal) are experienced, the woman or the woman's physician can adjust the dose to the previous week's dose or to 500mg metformin (whichever is the greater) and wait for a week before increasing the dosage again. They may also recommend to minimize adverse effects that the women take the treatment in the evening as the maximum recommended dose is 2000mg daily, taken as one dose in the evening.

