# MONTHLY STUDY VISITS (+/- 7 days)

Approximately 1 month (plus or minus seven days) after the commencement of study treatment (and every 4 weeks thereafter until delivery) a study visit will be conducted. During the visit the study team will collect information on any side effects, adverse events and pregnancy complications.

Adverse events (AE) will be recorded in the eCRF, and serious adverse events (SAEs) will be recorded on the SAE form as per section 10. Patients will also be asked to return their empty medication packages and unused medication to each visit. They will be asked if they are complying with their study medication and the diary reviewed, if available.

A further drug supply (sufficient for up to 5 weeks of treatment) will be prescribed and dispensed at each study visit, as required.

The number of monthly antenatal study visits completed for each woman will depend on the gestation at which the woman was recruited i.e. if consented and randomised at 12 weeks we would anticipate 8 antenatal visits (consent at 12 weeks plus a monthly visit at each gestational time point: 16/20/24/28/32/36 and 40 weeks maximum) to be conducted and recorded.

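### The first dispensing covers 4 weeks, but the first visit may fall 7 days after the nominal month; if the bottles are sized to the titration, an adherent woman seen late in the window runs out of tablets

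*Protocol*

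**What the plan says.** Four statements in the protocol bear on the first treatment interval.

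- **First supply.** Section 9.2 (Randomisation): "Medication will be dispensed in HDPE plastic bottles with sufficient supply for 4 weeks of treatment". Section 8.1.3 gives a general rule: "sufficient bottles for one month supply will normally be dispensed to a participant at any one time".
- **First visit.** Section 9.2 (Monthly study visits) places it "Approximately 1 month (plus or minus seven days) after the commencement of study treatment". Visits then follow every 4 weeks. The worked example for a woman entering at 12 weeks lists "a monthly visit at each gestational time point: 16/20/24/28/32/36 and 40 weeks maximum", which points to a nominal first visit on day 28.
- **Later supply.** Same section: "A further drug supply (sufficient for up to 5 weeks of treatment) will be prescribed and dispensed at each study visit".
- **Dose.** Section 8.3 steps up by one tablet a day each week, from one tablet in week 1: "In week 4 there will be a final increment to a total daily dose of 2000mg". The dose then stays at 4 tablets a day until delivery. A woman with side effects may step down and "wait for a week before increasing the dosage again".

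The protocol does not state the number of tablets per bottle, an overage for the first supply, or a way to obtain more tablets between visits.

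**The concern.** The allowance at study visits fits the visit window: 4 weeks plus 7 days is 5 weeks. The first interval has the same window, but its stated supply has no such margin. A woman who attends late, yet within the protocol, may therefore have no tablets for the last days before her visit. On the planned titration those days come just after she has reached the full dose.

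Adherence is specific objective C and secondary endpoint C, measured from the diary and returned tablets. Days without stock would count as days not taken unless they are separated out. A feasibility study that is meant to inform a larger trial should not create missed treatment through its own dispensing schedule.

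**Working it through.** The protocol gives a duration of supply and no tablet count, so there is no figure of its own to reproduce. The check compares tablets scheduled with tablets supplied.

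**Inputs.** Section 8.3: 1, 2, 3 and 4 tablets a day in weeks 1 to 4, then 4 a day. Section 9.2: first visit at 1 month plus or minus 7 days, counted from the start of treatment. Because the visit is timed from that start, the 48 hours allowed between randomisation and first dose use up no supply.

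**Tablets scheduled.** By day 28: 7 × (1 + 2 + 3 + 4) = 70. By a later day d: 70 + 4 × (d − 28).

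**Supply of 70 tablets (assumption: 4 weeks counted on the titration).**

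| Visit day | Reading | Scheduled | Short by | Days without tablets | 70 as share of scheduled |
|---|---|---|---|---|---|
| 28 | on time, 28-day month | 70 | 0 | 0 | 100% |
| 30 or 31 | on time, 30- or 31-day month | 78 or 82 | 8 or 12 | 2 or 3 | 90% or 85% |
| 35 | latest, 28-day month | 98 | 28 | 7 | 71% |
| 37 or 38 | latest, 30- or 31-day month | 106 or 110 | 36 or 40 | 9 or 10 | 66% or 64% |

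**Supply of one month as in section 8.1.3, with the month read the same way for supply and visit.** For 30 days: 106 − 78 = 28. For 31 days: 110 − 82 = 28. The gap is again the 7-day window at 4 tablets a day.

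**Larger first supplies.**
- 98 tablets (5 weeks on the titration) last to day 35. That leaves no gap for a 28-day month, but 106 − 98 = 8 or 110 − 98 = 12 tablets short on day 37 or 38.
- 112 tablets (4 weeks at 4 a day: 28 × 4) leave 112 − 70 = 42 at day 28, enough for 10 full days, to day 38. No reading of the window produces a gap.

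**One increment delayed by a week for side effects.** Tablets used by day 35 are 7 × (1+1+2+3+4) = 77, 7 × (1+2+2+3+4) = 84 or 7 × (1+2+3+3+4) = 91. Against 70 supplied, the shortfall falls from 28 to 7, 14 or 21.

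**Share of the whole course (assuming delivery at 40 weeks).** Entry at 12 weeks: 70 + 24 × 28 = 742 tablets. Entry at 28 weeks: 70 + 8 × 28 = 294. A shortfall of 28 is 3.8% and 9.5% of these; a shortfall of 40 is 5.4% and 13.6%.

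**The case against.** The strongest answer is that the gap depends on a number the protocol does not give. Supply is described in bottles, packed centrally, and nothing says the first bottles are counted to the titration. A supply sufficient for 4 weeks may be read as a minimum, section 8.1.3 says only what is normally dispensed, and no passage forbids more at randomisation. With 112 tablets there is no gap. This stands, and it makes the point conditional. It does not remove it: where the protocol wanted a margin for the visit window, at the study visits, it wrote one, and the first dispensing has none. The working practice document promised in section 8.1.5 sits under release to site and cannot be assumed to settle what each woman receives.

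It is also true that step-downs, temporary stops and missed doses stretch the supply, so the full shortfall needs full adherence and attendance late in the window. The protocol gives no basis for saying how often that will happen. The women most exposed are those who take every tablet.

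Days without stock may be traceable. Section 7.1 has the pack number entered in the participant's "medication record as well as in the drug accountability logs", and there is a daily diary. These could help separate stock-outs from non-adherence, but they cannot restore missed treatment.

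A reader might infer that women will run out, that the arms will be compared unfairly, or that the feasibility conclusion is at risk. The protocol supports none of these. The tablet count is unknown, the schedule is the same in both arms, section 11.2 rules out formal comparisons between arms, and the primary endpoint is a recruitment ratio.

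**Conclusion.** The point holds in conditional form and is minor. The stated first supply fits the protocol's own visit window badly. If that supply is 70 tablets, a fully adherent woman on the planned titration can be without tablets for up to 7 days (28-day month) or 9 to 10 days (30- or 31-day month) while attending as permitted. The 28-day reading is the better supported, because of the 4-weekly schedule. A visit by day 28 produces no gap, and neither does a first supply of 112 tablets.

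What is affected is one stretch of early treatment and a secondary endpoint reported descriptively. The change is worth making because it is simple and cheap.

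**What to change.** Choose one of two changes:

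- In section 9.2 (Randomisation), dispense at least 5 weeks' supply (98 tablets on the section 8.3 titration), and state the first visit as 4 weeks plus or minus 7 days. The two belong together, because 98 tablets suffice only if the month is fixed at 28 days.
- Or state that the first supply is 112 tablets, which covers every reading of the window. If that is already the intention, only the wording needs to change.

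In either case, make the supply wording in sections 8.1.3 and 9.2 agree.

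The cost, measured against a 70-tablet supply, is 98 − 70 = 28 to 112 − 70 = 42 extra tablets per woman, or 2,800 to 4,200 for 100 women. This should be counted as a real cost: unused tablets are returned and counted, and the protocol does not provide for reissuing them.

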# MONTHLY STUDY VISITS (+/- 7 days)

Approximately 1 month (plus or minus seven days) after the commencement of study treatment (and every 4 weeks thereafter until delivery) a study visit will be conducted. During the visit the study team will collect information on any side effects, adverse events and pregnancy complications.

Adverse events (AE) will be recorded in the eCRF, and serious adverse events (SAEs) will be recorded on the SAE form as per section 10. Patients will also be asked to return their empty medication packages and unused medication to each visit. They will be asked if they are complying with their study medication and the diary reviewed, if available.

A further drug supply (sufficient for up to 5 weeks of treatment) will be prescribed and dispensed at each study visit, as required.

The number of monthly antenatal study visits completed for each woman will depend on the gestation at which the woman was recruited i.e. if consented and randomised at 12 weeks we would anticipate 8 antenatal visits (consent at 12 weeks plus a monthly visit at each gestational time point: 16/20/24/28/32/36 and 40 weeks maximum) to be conducted and recorded.

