# 2.2.2 Secondary Endpoints

- A. Number of eligible women who are recruited into the study.
- B. Proportion of pregnant women presenting at or before 28+0 weeks gestation [when the intervention will be started].
- C. Adherence to therapy (ascertained by review of diary and returned study medication)
- D. Proportion of women in each of the placebo group and the active group (if tested prior to starting metformin) who have gestational diabetes between 24+0-30+6 weeks
- E. Ability to measure key clinical variables:
  - The incidence of gestational diabetes and pregnancy hypertensive disorders in women with BMI  $\ge$  26 kg/m^2in this setting
  - Feasibility of recruitment and randomisation
  - The proportion of women who present early in pregnancy (<20 weeks gestation) and are eligible for recruitment
  - The proportion of eligible women (and clinicians) are willing to participate in the study and be randomised (or randomise) to metformin or placebo?
  - In what proportion of women can we record other secondary outcomes planned for the substantive trial
  - The proportion of women who have an ultrasound scan before 20 weeks gestation so that gestational age can be determined.
  - The resources are required for outcome data ascertainment and collection
- F. Proportion of women lost to follow up for the primary and secondary outcomes.
- G. Determination of an appropriate method by which we can identify eligible women and avoid double randomisation to address co-enrolment (i.e. GPS home identifiers, thumb or finger print).

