#### 4.3 EXCLUSION CRITERIA

- A. Conditions identified in the current pregnancy, which exclude study participation:
  - Women with a BMI < 26 kg/m^2
  - Pregnancy gestation > than 28+0 weeks
  - Women who are known to have a multiple pregnancy at the time of trial entry

PAPAGENO: Protocol Version 1.0 07/03/2019 Page 16 of 46

- Women who are currently lactating
- Women known to have diabetes
- Women who have been taking HIV antiretroviral medication for less than 6 months
- Women currently taking dolutegravir
- Acute conditions at the time of trial entry with the potential to alter renal function such as:
  - Dehydration sufficient to require intravenous infusion
  - severe infection
  - o shock

0

- o intravascular administration of iodinated contrast agents
  - acute or chronic diseases which may cause tissue hypoxia such as:
    - cardiac or respiratory failure,
    - Pancreatitis
    - recent myocardial infarction,
    - hepatic insufficiency, acute alcohol intoxication, alcoholism
- B. History of the following pre-existing conditions, at the time of trial entry:
  - Had a previous delivery of a baby <3rd centile for gestational age (e.g. a baby born ≥ 37 weeks gestation and the birthweight was ≤2.25KG)
  - A known history in a previous pregnancy of gestational diabetes (needing drug treatment)
  - A known history of conditions affecting either the heart, lungs, liver, kidney or brain, which require regular medication at the time of recruitment
  - A known history of allergy to metformin or to any of the ingredients as listed in the current Summary Products Characteristics (SPC))
  - Known liver failure or dysfunction at the time of trial entry
  - Known severe renal failure or dysfunction at the time of trial entry
  - Known (any type of) acute metabolic acidosis (such as lactic acidosis, diabetic ketoacidosis)
  - A previous known diabetic pre-coma
  - Previous known severe renal failure (GFR < 30 mL/min).

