# WEEK 24+0 – 30+6 GESTATION VISIT

At one of the monthly visits, which occurs at or between 24+0 and 30+6 weeks gestation. A 75g OGTT (baseline and 2 hour sample) will be performed (as per the working practice document) and stored locally for future investigations.

Prior to the visit, the woman will be given written information and have this read to her (if applicable) which ask her to fast (take no food, only water) for a period of 8-12 hours before the appointment. With the exception of the 75g glucose load, the woman will remain fasted until after the 2 hour blood sample is taken.

The results of the glucose tolerance test is not a routine test, and the results will be concealed from the woman and from her caregivers until the end of the study. An additional OGTT (outwith the trial) can be performed for clinical reasons at any time if required by the local physician. If a participant develops gestational diabetes during the study, she will be asked to stop the study treatment (IMP) and will be referred to her obstetrician for further advice and treatment, which may include diet metformin and/or insulin. The details of any treatments and reasons for stopping the IMP will be recorded in the eCRF. Following local procedures the clinical care team may also conduct tests to identify other pregnancy related diseases such as a blood pressure monitoring, urine test strip and blood samples to screen for e.g. pregnancy induced hypertension, pre-eclampsia or anaemia. Any diseases identified in a participant/ fetus/ baby will be recorded following the adverse events reporting.

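### Endpoint D calls for active-arm women tested before metformin, but the schedule places no OGTT before treatment, and the 30+6 limit for the test fits poorly with entry up to 28+0

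*Protocol*

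**What the plan says.** Section 2.2.2, endpoint D, covers the placebo group and "the active group (if tested prior to starting metformin) who have gestational diabetes between" 24+0 and 30+6 weeks. Objective D in section 2.1.2 and the Trial Summary carry the same condition.

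Four parts of the protocol decide when that test can happen:

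- Section 9.2, Randomisation, on the treatment start date: "this should be no later than 48 hours after randomisation".
- Section 9.2, Monthly Study Visits: the first visit is "Approximately 1 month (plus or minus seven days) after the commencement of study treatment". Later visits follow at 4-week intervals.
- Section 9.2, Week 24+0 to 30+6 Gestation Visit: the OGTT is done "At one of the monthly visits, which occurs at or between" those two gestations.
- The Table of Study Visits marks the glucose tolerance test only in the 24 to 30 week column. That column also has diary review and return of unused drug, so it describes a woman already on treatment. The baseline assessments listed under Consent contain no glucose test.

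Entry is open to 28+0 (section 4.2). The matching exclusion in section 4.3 is "Pregnancy gestation > than 28 +0 weeks".

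**The concern.** A stated objective and endpoint depend on a measurement that the stated procedures never take. Pre-treatment active-arm results would be a second source of information on untreated gestational diabetes, and section 11.1 says that the prevalence estimates will inform the large trial. As scheduled, that source is empty.

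Separately, a woman may enter at 28+0 and then wait about four weeks for a test whose window closes less than three weeks after she entered. In a feasibility study this matters beyond the lost values. Endpoints E and F ask whether outcomes can be measured and how many women are lost. An OGTT missed because the calendar did not allow it says nothing about whether women attend or whether clinics can do the test, yet it could be read that way. Such misses would also concentrate in late presenters.

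**Working it through.** **Inputs.** Gestation is counted in days.

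- Entry: 12+0 (day 84) to 28+0 (day 196), sections 4.2 and 4.3.
- OGTT window: 24+0 (day 168) to 30+6 (30 × 7 + 6 = day 216), section 9.2.
- Delay from randomisation to treatment: 0 to 2 days, section 9.2.
- First monthly visit: about one month after treatment starts, ± 7 days, then every 4 weeks, section 9.2.
- Allocation 1:1 (section 7.1) of 100 women, so 50 per arm (section 11.1).

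**The protocol's own figure.** Consent at 12 weeks followed by visits every 4 weeks to 40 gives 12, 16, 20, 24, 28, 32, 36 and 40. That is 8 visits, as section 9.2 states, so 28 days is the protocol's nominal interval.

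**Step 1: an OGTT before metformin.** The earliest first visit is 28 − 7 = 21 days after treatment starts. Scheduled trial OGTTs before metformin in the active arm: 0 of 50. This needs no assumption about when women enter.

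**Step 2: the last randomisation day that still allows a test by 30+6.** With start delay *d* and first visit *v* days after the start, the last day is *r* = 216 − *v* − *d*.

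| First visit | Start same day (*d* = 0) | Start 48 h later (*d* = 2) |
|---|---|---|
| Nominal, day 28 | 188 = 26+6 | 186 = 26+4 |
| Earliest allowed, day 21 | 195 = 27+6 | 193 = 27+4 |
| Latest allowed, day 35 | 181 = 25+6 | 179 = 25+4 |

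If one month is read as 30 or 31 days, the same-day cut-offs become 26+4 or 26+3 nominally, and 27+4 or 27+3 with the full minus seven days.

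Earlier entrants are not affected on the nominal schedule. The window spans 216 − 168 + 1 = 49 days and visits are 28 days apart, so at least one visit falls inside it. Only randomisation from 27+0 to 28+0 misses it.

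**Step 3: how many women.** The protocol gives no distribution of gestation at entry. The shares below assume uniform entry, counted in whole days, for three assumed ranges.

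| | 12–28 wk (113 days) | 20–28 wk (57 days) | 24–28 wk (29 days) |
|---|---|---|---|
| Miss at nominal visit, same-day start (27+0 to 28+0, 8 days) | 8/113 = 7% | 8/57 = 14% | 8/29 = 28% |
| Must miss, same-day start (28+0 only, 1 day) | 1/113 = 0.9% | 1/57 = 1.8% | 1/29 = 3.4% |
| Must miss, 48 h delay (27+5 to 28+0, 3 days) | 3/113 = 2.7% | 3/57 = 5.3% | 3/29 = 10% |

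Among 50 placebo women, the nominal miss is 50 × 0.07 = 3.5 over 12–28 weeks and 50 × 0.14 = 7 over 20–28 weeks. The unavoidable miss with same-day start is below one woman in both cases.

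**The case against.** **The clause is conditional.** Endpoint D says only what to do if such a test exists, and section 9.2 allows an additional OGTT outside the trial at any time for clinical reasons. So a reader who infers that no active-arm woman could ever be tested before metformin goes too far. But a clinically prompted test is neither planned nor systematic, and a proportion based on it would describe a selected few. The condition does not supply a denominator.

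**The consent visit might count as a monthly visit.** It is one of the eight antenatal visits in section 9.2. That sentence, however, counts consent plus the monthly visits, and neither the baseline list nor the visit table places an OGTT there.

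**The visit window rescues most late entrants.** This stands. A reader might infer that everyone randomised after 26+6 misses the test. The protocol does not support that: minus seven days is expressly allowed, and women randomised from 27+0 to 27+6 can be tested in time if treatment starts the same day and the visit is brought forward. What remains is that nothing tells sites to do so, and that a late visit or delayed start moves the cut-off the other way.

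**Little depends on it.** This largely stands. The primary endpoint is the recruitment ratio. Section 11.2 estimates prevalence within the placebo group only and plans no formal comparison between arms. Nor does the protocol say that a woman who attends but is tested outside the window counts as lost to follow-up; that is a risk to close, not something it states.

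**Conclusion.** Two inconsistencies stand. First, the active-arm part of objective and endpoint D has no scheduled data (0 of 50); this follows from the text alone. Second, the 28+0 entry limit and the 30+6 OGTT limit do not fit the visit schedule. The nominal cut-off is 26+6, and the cut-off with the full minus seven days is 27+6 (27+4 with a 48-hour start delay). The resulting shares, about 7% nominally and 1% unavoidably over 12 to 28 weeks, or 14% and 2% over 20 to 28 weeks, depend on assumed uniform entry and same-day start.

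Severity is moderate. The first inconsistency leaves the primary endpoint and the section 11.2 prevalence analysis untouched. The second can remove some late-entering placebo women from that analysis, but nearly all of that loss can be avoided by timing the first visit early.

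A reader might also infer that pre-dose active-arm results could simply be added to the placebo group for precision. That is not supported. Suppose a quarter of women enter in the last 4 of the 16 entry weeks, and 35 placebo women remain after the 30% dropout of section 11.1 (50 × 0.7). Of these, 35 × 0.25 = 8.75 are late entrants. Adding 12 late-entering active-arm women makes the late share (8.75 + 12)/47 = 44% instead of 25%. The sum also mixes placebo women after dropout with active-arm women before it.

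**What to change.** Reconcile the Trial Summary and sections 2.1.2, 2.2.2, 4.2, 9.2 and the Table of Study Visits in one of two ways.

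1. **Supply the data.** Do the study OGTT before the first dose, in both arms, for women randomised at 24+0 or later, and keep the monthly-visit OGTT for earlier entrants. This also removes the window conflict, because those women are already between 24+0 and 28+0. Report the active-arm pre-dose results separately, or standardised for gestation at entry, and not simply pooled with placebo. No test is added, and under section 10.1 glucose is analysed only after the last visit, so concealment is unaffected. The costs are real: an 8 to 12 hour fast and a 2-hour test at entry, which may hinder same-day consent and so recruitment, the primary endpoint. For these women the single test would also be a baseline value and not an on-treatment outcome.

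2. **Remove the promise.** Delete the active-arm clause from objective and endpoint D. State that where the nominal first visit would fall after 30+6 (randomisation after 26+6, or after 26+4 with a 48-hour start delay), it is brought forward within the permitted seven days so that the OGTT falls by 30+6. Report women who cannot meet this as missed by schedule, not as lost to follow-up. This changes text only, but gives up pre-treatment active-arm data and leaves a small unavoidable gap at the entry limit.

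Either way, record gestation at the OGTT and at entry, so that the actual share affected replaces the assumed one.
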